#### 8.3.1.3 Tinnitus Functional Index (TFI)

The Tinnitus Functional Index (TFI) will be measured at visit 1, visit 2, visit 3 and visit 4.

The actual patient reported outcome (PRO) value and change from baseline TFI will be summarized by visits and treatment groups.

TFI will be analyzed as a composite score and for the following individual subscales: Intrusiveness, Sense of control, Cognition, Sleep, Auditory, Relaxation, Quality of life, and Emotional.

This document is confidential and proprietary to Sponsor and EA and for restricted circulation and access only. No part of it may be transmitted, reproduced, published or used by any person/s without prior written authorization.

Version No.: Final 1.0

Page 21 of 38

Sponsor Study No: SPI-1005-251 Sponsor Name: Sound Pharmaceuticals, Inc.

CRON ACUNOVA

NLS Study Code: SPI -1005 -251 Short Title of Study: SPI -1005 -251 (Sound Pharmaceuticals, Inc)

The overall total score will be calculated by the sum of all valid answers from both TFI pages and will be divided by the number of questions for which that respondent provided valid answers and then multiplied by 10.

| SUBSCALE NAME         | ITEMS IN SUBSCALE  |
|-----------------------|--------------------|
| INTRUSIVE             | #1, #2, #3         |
| SENSE OF CONTROL      | #4, #5, #6         |
| COGNITIVE             | #7, #8, #9         |
| SLEEP                 | #10, #11, #12      |
| AUDITORY              | #13, #14, #15      |
| RELAXATION            | #16, #17, #18      |
| QUALITY OF LIFE (QOL) | #19, #20, #28, #22 |
| EMOTIONAL             | #23, #24, #25      |

Each of the 8 subscales consists of 3 items (except for the Quality of life subscale, which consists of 4 items). For subscale scores to be valid no more than 1 item should be omitted. Computation of subscale scores is calculated as:

1) Sum all respondent's valid answers for a given subscale.

2) Divide that number by the number of valid answers that were provided by that respondent for that subscale.

3) Multiply by 10. For the respondent in question, this procedure generates a subscale score in the range 0-100 for each valid subscale.

Overall TFI score is not valid if the respondent omits seven or more items. To be considered a valid measure of tinnitus severity, the respondent must answer at least 19 items.

The TFI data will be analyzed with a mixed-effects model for repeated measures, and a post-hoc Bonferroni correction analysis with significance set to 0.05. The calculated change of TFI data will be calculated as the difference of the PRO value at baseline and the PRO value at each post baseline timepoint. The improvement will be considered only if the difference between post baseline and baseline value is  $\geq 10$  pts. The final processed data will be analyzed using a chi-square test or Fisher's Exact test to assess the improvement between treatment groups.

This document is confidential and proprietary to Sponsor and EA and for restricted circulation and access only. No part of it may be transmitted, reproduced, published or used by any person/s without prior written authorization.

Statistical Analysis Plan Version No.: Final 1.0

Page 22 of 38

Sponsor Study No: SPI-1005-251 Sponsor Name: Sound Pharmaceuticals, Inc.

CRON ACUNOVA

NLS Study Code: SPI -1005 -251

Short Title of Study: SPI-1005-251 (Sound Pharmaceuticals, Inc)

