#### 8.3.1.5 Vertigo Symptom Scale

Vertigo Symptom Scale (VSS) will be measured at visit 1, visit 2, visit 3 and visit 4.

The actual patient reported outcome (PRO) value and change from baseline for VSS will be summarized by visits and treatment groups.

VSS will be analyzed for Total Scale, Vertigo/balance sub-scale and Autonomic/anxiety sub-scale. The Vertigo/balance sub-scale will be calculated as the sum of questions 1, 3, 4, 6, 8, 10, 13 and 15. The Autonomic/anxiety sub-scale will be calculated as the sum of questions 2, 5, 7, 9, 11, 12 and 14. The range for the Vertigo/balance sub-scale will be 0 - 32 and the range for Autonomic/anxiety sub-scale will be 0 - 32.

VSS data will be analyzed with a mixed-effects model for repeated measures, and a post-hoc Bonferroni correction analysis with significance set to 0.05.

The calculated change of VSS data will be calculated as the difference of the PRO value at baseline and the PRO value at each post baseline timepoint. The improvement will be considered only if the difference between post baseline and baseline value is  $\geq 6$  pts. The final processed data will be analyzed using a chi-square test or Fisher's Exact test to assess the improvement between treatment groups.

This document is confidential and proprietary to Sponsor and EA and for restricted circulation and access only. No part of it may be transmitted, reproduced, published or used by any person/s without prior written authorization.

Version No.: Final 1.0

ECRON ACUNOVA Sponsor Study No: SPI-1005-251 Sponsor Name: Sound Pharmaceuticals, Inc.

NLS Study Code: SPI-1005-251

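### As supplied, the SAP's table for the TFI Quality of life subscale names item #28 of a 25-item questionnaire and leaves #21 unassigned, so literal scoring would use three items instead of four

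*SAP*

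**What the plan says.** SAP 8.3.1.3 plans the subscales as analyses in their own right: "TFI will be analyzed as a composite score and for the following individual subscales", and Quality of life is one of the eight named. The item table gives that subscale as "QUALITY OF LIFE (QOL) | #19, #20, #28, #22". The other seven subscales take #1 to #18 and #23 to #25.

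The section then fixes the sizes: "Each of the 8 subscales consists of 3 items (except for the Quality of life subscale, which consists of 4 items". A subscale score is the mean of the valid answers times 10, subject to an omission limit: "For subscale scores to be valid no more than 1 item should be omitted". For the total score the limits are "Overall TFI score is not valid if the respondent omits seven or more items" and "the respondent must answer at least 19 items". The total does not use the subscale table: "The overall total score will be calculated by the sum of all valid answers from both TFI pages".

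SAP 8.3.1.5 splits the Vertigo Symptom Scale into eight Vertigo/balance questions and seven Autonomic/anxiety questions. It gives 0-32 for the first, and for the second says "the range for Autonomic/anxiety sub-scale will be 0 - 32". SAP 5.1 and 6.2.1 give the VSS total as 0-60.

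**The concern.** The table points to an item number that the questionnaire, by the SAP's own counts, does not have, and it leaves a real item in no subscale. The slip could go unnoticed because the scoring rule tolerates one omitted item per subscale. A program that treated #28 as permanently missing would return a plausible Quality of life score from three items, with no flag. It would also have used up the one permitted omission, so a patient who skipped one of the three remaining items would lose a score that the four-item rule accepts. SAP 7.5.1 provides for no imputation, so that score would stay missing.

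The VSS range is a second, smaller inconsistency: a seven-item subscale is given the same maximum as an eight-item one.

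**Working it through.** **Length of the TFI, from two independent statements in SAP 8.3.1.3**

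- Subscale sizes: 7 × 3 + 1 × 4 = 25 items.
- Validity rule: seven or more omissions invalidate the total, so at most 6 may be omitted, and at least 19 must be answered. 19 + 6 = 25. A form of 24, 26, 27 or 28 items would need a minimum of 18, 20, 21 or 22 answers, so only 25 fits.

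**Items in the table**

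- Listed: #1 to #20, #22 to #25, and #28, which is 25 entries.
- Outside 1-25: #28. In 1-25 but not listed: #21.
- Replacing #28 with #21 makes the eight subscales cover items 1-25 exactly once.

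**Effect on the score if #28 is coded literally as always missing**

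Items run 0-10, as SAP 5.1 states for item 2 and as the multiplication by 10 to a 0-100 scale implies. Let m be the mean of #19, #20 and #22, and x the answer to #21.

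- Four-item score: 10 × (3m + x)/4
- Three-item score: 10 × m
- Difference: 10 × (m − x)/4 = 2.5 × (m − x)

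| Gap between item 21 and the mean of the other three | Error on 0-100 |
|---|---|
| 0 | 0 |
| 2 | 2.5 × 2 = 5 |
| 4 | 2.5 × 4 = 10 |
| 10 (the maximum) | 2.5 × 10 = 25 |

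The documents give no item-level data, so the likely gap is unknown. The 25-point maximum needs item 21 at one end of its scale and the other three all at the opposite end.

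**Effect on validity, with #28 counted as an omission**

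- #19, #20 and #22 all answered: one counted omission, so the score is accepted, whatever was answered to #21.
- One of #19, #20 or #22 skipped and #21 answered: two counted omissions, so invalid. Under the four-item rule there is one omission, and the score is valid.

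The documents give no skip rate. With 120 patients, each percentage point is 0.01 × 120 = 1.2 patients at a visit. As pure assumptions, 1% would be 1.2 patients, 5% would be 6 and 10% would be 12.

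**VSS ranges**

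- The two question lists cover 1 to 15 once each, in a split of 8 and 7.
- A total of 0-60 over 15 equally scored questions gives 60/15 = 4 points per question.
- Vertigo/balance: 8 × 4 = 32, which reproduces the stated 0-32.
- Autonomic/anxiety: 7 × 4 = 28, not 32.
- The stated maxima add to 32 + 32 = 64. The corrected ones add to 32 + 28 = 60, which agrees with the total.

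**The case against.** The strongest objection is that the TFI point rests on one digit. The text at hand was converted from PDF, and a 1 can be misread as an 8. The same files show damage of this kind: the protocol synopsis gives the VSS responder threshold as 26 points where SAP 5.1 and 6.2.1 give 6 or more, and SAP section 13 shows one table number in two different forms. This stands. The rest of the TFI table is clean, so a misread cannot be shown, but it cannot be excluded either. The point is therefore conditional on the SAP source page.

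A second objection is that little depends on it. That also stands. The total uses every valid answer, Tinnitus Loudness is item 2, and none of the five primary responder measures in SAP 6.2.1 uses a subscale. No table or figure title in SAP sections 13 and 14 names a subscale. What remains is that 8.3.1.3 does plan the subscale analysis, and a final SAP should not carry a wrong scoring rule for it.

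A third objection is that a programmer would notice. The section says that Quality of life has four items, and #21 is the only gap in the numbering. That is a fair expectation, but not a safeguard written into the plan.

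Readers might also infer that the subscale cannot be computed at all, or that it would be wrong for most patients. The documents support neither. Literal scoring gives a three-item result, and whether that happens, and how far it is off, depends on the program and on answers not in hand.

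**Conclusion.** As supplied, the Quality of life row in SAP 8.3.1.3 contradicts the SAP's own item counts. If the source page agrees, the row is a wrong scoring rule for one planned subscale. Followed literally, it would shift the score by 2.5 times the gap between item 21 and the mean of the other three items, at most 25 points on 0-100, and would wrongly invalidate patients who skipped exactly one of #19, #20 or #22 and answered #21. This rests on three assumptions: the digit is not a conversion error, the program keeps the table as printed, and it counts #28 as an omitted item.

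The reach stops at that subscale. The TFI total, Tinnitus Loudness and all primary responder endpoints are unaffected.

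The VSS range is a clerical error only. A reader might infer that impossible Autonomic/anxiety scores of 29 to 32 would pass a data check. The SAP describes no such check, the subscale is correctly defined as a sum of seven named questions, and the stated range enters no calculation.

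**What to change.** 1. Check the digit on the SAP source page and against the administered TFI form. If the page reads #21, the TFI point falls away.
2. If it reads #28, replace it with #21 in the table in 8.3.1.3. Confirm that the scoring program uses #19 to #22 and applies the one-omission limit to all four items.
3. In 8.3.1.5, state the Autonomic/anxiety range as 0-28, so that the two maxima add to 60.

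The cost is one table cell, one number and a short check of the scoring program. If subscale results have already been produced from the literal table, only the Quality of life derivation has to be rerun.

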#### 8.3.1.4 Tinnitus Loudness

Tinnitus loudness (TL) will be measured at visit 1, visit 2, visit 3 and visit 4. TL is assessed from question number two of the TFI.

The actual patient reported outcome (PRO) value and change from baseline for TL will be summarized by visits and treatment groups. TL data will be analyzed with a mixed-effects model for repeated measures, and a post-hoc Bonferroni correction analysis with significance set to 0.05. The calculated change of TL data will be calculated as the difference of the PRO value at baseline and the PRO value at each post baseline timepoint. The improvement will be considered only if the difference between post baseline and baseline value is  $\geq 2$  pts. The final processed data will be analyzed using a chi-square test or Fisher's Exact test to assess the improvement between treatment groups.

#### 8.3.1.5 Vertigo Symptom Scale

Vertigo Symptom Scale (VSS) will be measured at visit 1, visit 2, visit 3 and visit 4.

The actual patient reported outcome (PRO) value and change from baseline for VSS will be summarized by visits and treatment groups.

VSS will be analyzed for Total Scale, Vertigo/balance sub-scale and Autonomic/anxiety sub-scale. The Vertigo/balance sub-scale will be calculated as the sum of questions 1, 3, 4, 6, 8, 10, 13 and 15. The Autonomic/anxiety sub-scale will be calculated as the sum of questions 2, 5, 7, 9, 11, 12 and 14. The range for the Vertigo/balance sub-scale will be 0 - 32 and the range for Autonomic/anxiety sub-scale will be 0 - 32.

VSS data will be analyzed with a mixed-effects model for repeated measures, and a post-hoc Bonferroni correction analysis with significance set to 0.05.

The calculated change of VSS data will be calculated as the difference of the PRO value at baseline and the PRO value at each post baseline timepoint. The improvement will be considered only if the difference between post baseline and baseline value is  $\geq 6$  pts. The final processed data will be analyzed using a chi-square test or Fisher's Exact test to assess the improvement between treatment groups.

This document is confidential and proprietary to Sponsor and EA and for restricted circulation and access only. No part of it may be transmitted, reproduced, published or used by any person/s without prior written authorization.

Version No.: Final 1.0

ECRON ACUNOVA Sponsor Study No: SPI-1005-251 Sponsor Name: Sound Pharmaceuticals, Inc.

NLS Study Code: SPI-1005-251

#### 8.4 Safety Analysis

#### 8.4.1 Adverse Events

Adverse Events will be coded using the Medical Dictionary of Regulatory Activities (MedDRA version 19.1), the coded terms will be used for summarizing the AE(s).

Page 23 of 38

An AE will be considered as treatment-emergent if the time of onset is on or after the time of the first randomized study drug administration. AEs with unknown start dates will be counted as treatment-emergent unless the AE resolution date is prior to the study drug start date. If the start date is partially missing, AE will be considered treatment-emergent unless the known part of the start date or the end date rules out that it occurred after the start of the study drug.

An overall summary table which summarizes, the number and percentages of patients with adverse events, treatment emergent adverse events, serious adverse events, adverse events leading to death and adverse events related to study drug will be provided by treatment groups.

Patients experiencing any adverse events will be summarized by Preferred Term (PT), SOC and treatment. Furthermore, listings of SAEs and AEs that lead to withdrawal will be provided. The number and percentage of patients with at least one TEAE, SAE and discontinuation of study treatment due to AE (DAE) will be summarized by system organ class, preferred term and treatment group.

Adverse Events will be summarized by System Organ Class, Preferred Term and Treatment for Any Adverse Events, Serious Adverse Events, Adverse Events leading to medication discontinuation, Adverse leading to death, Adverse Events by severity, Adverse Events by outcome and Adverse Events by relationship.

A patient experiencing the same AE multiple times will be counted only once for that preferred term. Similarly, if a patient experiences multiple AEs within the same system organ class that patient will be counted only once in that system organ class. In summaries by severity or by relationship, if a patient has the same AE on multiple occasions, the highest severity, and the closest relationship to study drug, respectively, will be used for summary.

All information pertaining to adverse events noted during the study regardless of treatment emergent or not will be listed by patient, detailing verbatim, preferred term, system organ class, start date, stop date, TEAE status, severity, outcome, action taken and causal relationship to the study drug.

#### 8.4.2 Clinical Laboratory Evaluations

Blood samples for clinical safety laboratory assessments will be collected at the following time Visit 1, Visit 2, Visit 3 and Visit 4. The following parameters will be analyzed under these categories:

| Hematology  | Chem                 | nistry               |
|-------------|----------------------|----------------------|
| RBC         | Sodium               | Albumin              |
| Hematocrit  | Potassium            | AST (SGOT)           |
| Hemoglobin  | Chloride             | ALT (SGPT)           |
| Platelets   | Bicarbonate          | GGT                  |
| WBC         | Glucose              | Total bilirubin      |
| Noutrophile | Blood urea nitrogen  | Alkaline phosphatase |
| Neutrophils | (BUN) or Urea        |                      |
| Lymphocytes | Creatinine           | Uric acid            |
| Monocytes   | Calcium              | LDH                  |
| Basophils   | Magnesium            | Cholesterol          |
| Eosinophils | Inorganic phosphorus | Triglycerides        |
|             | Total protein        |                      |

Laboratory results will be summarized descriptively for actual and change from baseline values by visits and treatment for each category of clinical chemistry and hematology. In addition, baseline shift tables will be presented for the lab parameters by visits and treatments for laboratory categories, the results falling out of normal ranges will be classified as Normal, Abnormal High and Abnormal Low and will be used for the shift tables. The 'Normal', 'Abnormal Low' and 'Abnormal High' values are determined based on the laboratory normal ranges. The number and percentage of patients reaching 'Normal', 'Abnormal CS' and 'Abnormal NCS' results for laboratory parameters will be summarized All laboratory results will be listed in data listings, the abnormal values will be flagged in the listings.

This document is confidential and proprietary to Sponsor and EA and for restricted circulation and access only. No part of it may be transmitted, reproduced, published or used by any person/s without prior written authorization.

Version No.: Final 1.0

E ECRON ACUNOVA

Sponsor Study No: SPI-1005-251

Sponsor Name: Sound Pharmaceuticals, Inc.

NLS Study Code: SPI-1005-251 Short Title of Study

Short Title of Study: SPI-1005-251 (Sound Pharmaceuticals, Inc)

#### 8.4.3 Vital Signs

Vital signs will be measured at Visit 1, Visit 2, Visit 3 and Visit 4.

Page 25 of 38

The vital signs parameters include:

- Systolic Blood Pressure (mmHg)
- Diastolic Blood Pressure (mmHg)
- Pulse Rate (Beats/min)
- Oral Temperature (°C)

The actual and change from baseline vital signs parameters will be summarized descriptively by visits and treatment groups.

In addition, number and percentage of patients reaching 'Normal', 'Abnormal CS' and 'Abnormal NCS' results for vital signs parameters will be summarized by visits and treatment groups. Data listings will be presented for vital signs parameters.

Shift tables for the overall interpretation of vital signs parameters will be summarized by visits and treatment groups.

#### 8.4.4 Physical examination

Physical examination will be performed at Visit 1, Visit 2, Visit 3 and Visit 4. Physical examination will include an examination of skin, HEENT (Otoscopic exam) Head/ Eyes/ Ears/Nose/Throat/Thyroid, Respiratory, Cardiovascular, Abdomen, Musculoskeletal, Neurological (and reflexes), Gastrointestinal, Endocrine, Lymph nodes and others.

A summary of these findings, number and percentages of patients achieving 'Normal', 'Abnormal CS', 'Abnormal NCS' will be presented by visit, body system and treatment group. Results will also be listed.

#### 8.5 Pharmacokinetic Analysis

The PK analysis will be performed based on PK analysis population.

Three (3) mL of blood will be collected at visit 1, visit 2, visit 3 and visit 4. Study participants should be instructed to refrain from taking their morning dose until after their blood is drawn at Clinic Visit 2 and Clinic Visit 3. Sample collection times (actual clock time using 24:00) are to be recorded and will be captured in the CRF.

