|                                       | • Improvement in the Vertigo Symptoms Scale (VSS).  |  |  |  |  |
|                                       | The secondary objectives of this study are to determine the:  |  |  |  |  |
|                                       | • Pharmacokinetics of SPI-1005.   |  |  |  |  |
| Study Design                          | Randomized Double Blind Placebo Controlled Study of SPI-1005 in adult volunteers with Meniere's Disease (probable or definitive   |  |  |  |  |

| SPI-1005-251: CLINICAL TRIAL SYNOPSIS |   |  |  |  |
|---------------------------------------|---|--|--|--|
|                                       | diagnosis) with active symptoms in the months preceding study
enrollment. All subjects will undergo baseline audiometric testing and
have their severity of sensorineural hearing loss, tinnitus and vertigo
determined before initiating treatment. Subjects will be randomized to
treatment, either placebo or two different doses of SPI-1005 (1:1:1)
and treated for 28 days. Subjects will return to clinic 2 weeks after the
start of study drug to have safety assessments and to receive additional
study drug. Subjects will return to clinic at week 4 to have their
hearing loss, tinnitus and vertigo re-assessed, and again 4 weeks after
the end of study drug treatment. Therefore, 4 scheduled clinic visits
will be performed over an 8 week period. Audiometry will be
performed at baseline, at the end of the 4 week treatment period, and 4
weeks after treatment has stopped. The TFI and VSS will be
performed at all scheduled clinic visits. Subjects are allowed to
continue with their existing maintenance therapies (i.e. low salt diet,
thiazide diuretic, or other PRN medications) except for the use of oral
or locally injected steroids. New treatments should be avoided while
on study. |  |  |  |
| Study Centers                         | Approximately 12 U.S. sites will participate in this study  |  |  |  |
| Subjects                              | 120 male and female adults with probable or definitive Meniere's disease.   |  |  |  |

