| Inclusion
Criteria                 | 
 
Adult male and female patients, 18-75 years of age at the time of enrollment.
 
Diagnosis of probable or definitive Meniere's disease by AAO-HNS 1995 criteria (Section 12.1, APPENDIX I).
 
Two of three active symptoms including vertigo or disequilibrium, fluctuating hearing loss, or tinnitus within the 3 months prior to study enrollment.
 
Hearing loss of ≥30 dBHL at either 250, 500 or 1000 Hz.
 
Voluntary consent to participate in the study.
 
Male subjects that are willing to use condoms throughout the study period and 90-days following study completion even if not fertile.
 
Females of childbearing potential should either be sexually inactive (abstinent) for 14 days prior to screening and throughout the study or be using one of the following acceptable birth control methods: 
 
IUD in place for at least 3 months prior to study; or
 
Barrier method (condom or diaphragm) with spermicide for at least 14 days prior to screening through study completion; or
 
Stable hormonal contraceptive for at least 3 months prior
 
 
 
   |  |  |  |

| SPI-1005-251: CLINICAL TRIAL SYNOPSIS |  |  |  |  |
|---------------------------------------|--|--|--|--|
|                                       | 
 
to study and through study completion; or
 
Surgical sterilization (vasectomy) of partner at least 6 months prior to study enrollment.
 
Females of non-childbearing potential should be surgically sterile (bilateral tubal ligation with surgery at least 6 months prior to study enrollment, hysterectomy, or bilateral oophorectomy at least 2 months prior to study) or be at least 1 year since last menses.
 
 |  |  |  |
| Exclusion
Criteria                 |  |  |  |  |
| Study Duration                        | Estimated duration of 12 months  |  |  |  |
| Participant
Duration               | Participation for each study participants will be approximately 8 to 12 weeks across 4 clinic visits.  |  |  |  |
| Dose &
Regimen                     | Subjects will receive either SPI-1005 or matching placebo for 28 days.
Treatment will be taken orally BID. Doses include 200 mg or 400 mg
of ebselen or matching placebo in capsule form. Two week supplies
will be provided on Clinic Visit 1 and 2.   |  |  |  |

| SPI-1005-251: CLINICAL TRIAL SYNOPSIS |   |  |  |  |
|---------------------------------------|---|--|--|--|

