#### 8.2 Extent of Exposure and Compliance

#### 8.2.1 Treatment Exposure

Treatments will be dispensed at baseline to patients based on the randomized group assignments and the patients will receive the treatment for a duration of 28 days.

The earliest date of 'date of drug dispense' (Date of dispensing) from Study Drug Dispensing and Drug Accountability eCRF form, where the patient has:

• Answered 'Yes' to question, 'Study medication dispensed?' and,

Page 19 of 38

• Recorded at least one capsule used for the question, 'Number of capsules taken'

If the drug administration date is unavailable and the last dose date of the patient is only available, then the Randomization date will be considered as treatment start date.

The treatment end date is taken from the field:

- 'Date of last study medication taken' from 'Study Completion or Early Termination' page. If the date of last study drug administration is missing and there is evidence that the patient has taken study medication, last visit date will be considered as 'Treatment end date'.
- Duration of treatment exposure is derived as treatment end date treatment start date + 1

The duration of treatment exposure will be summarized descriptively by treatment group for safety population. Data listing will be presented for study drug administration.

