#### **Confidentiality Statement**

Statistical Analysis Plan Version No.: Final 1.0 **ECRONACUNOVA** 

Sponsor Study No: SPI-1005-251

Sponsor Name: Sound Pharmaceuticals, Inc.

| NLS Study Code: SPI -1005 -251 | Short Title of Study: SPI-1005-251 (Sound Pharmaceuticals, Inc) |
|--------------------------------|---|

Page 26 of 38

The patient listings as well as Patient's PK profile plots in actual and semi-logarithmic views will be prepared for the PK concentrations. Descriptive summary statistics table including geometric mean & CV% geometric mean will be presented by timepoints and treatment groups. In addition, mean  $\pm$  SD graphs will be prepared for the concentration by timepoints and treatment groups. Descriptive statistics including geometric mean & CV% geometric mean will be presented for the PK

parameters, AUC  $_{0-t}$  (mg. h/L) and  $C_{max}$  (mg/L).

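### If dosing stops after 28 days, a Visit 3 sample drawn in window on Day 30 or 31 is about 36 or 60 hours post-dose, yet SAP 8.5 summarises it with the 12-hour troughs

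*SAP*

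**What the plan says.** The protocol synopsis (PK Assessments) and SAP 6.1 both call the samples trough plasma levels. SAP 5.2 makes pharmacokinetics at each dose level the only secondary objective.

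- **Course.** Protocol synopsis, Dose & Regimen: "Subjects will receive either SPI-1005 or matching placebo for 28 days" and "Treatment will be taken orally BID". SAP 8.2.1 agrees: "patients will receive the treatment for a duration of 28 days".
- **Supply.** Protocol synopsis: "Two week supplies will be provided on Clinic Visit 1 and 2". SAP 6.1 also has drug dispensed at these two visits only. No capsule count or overage is given.
- **Windows.** Protocol 1.3 sets Visit 2 at Day 14 and Visit 3 at Day 28, each plus or minus 3 days. The same table marks study treatment at Visit 3.
- **Trough safeguard.** SAP 8.5 asks participants to "refrain from taking their morning dose until after their blood is drawn at Clinic Visit 2 and Clinic Visit 3". The clock time of the draw is recorded. No time of the preceding dose is named.
- **Summary.** SAP 8.5: "Descriptive summary statistics table including geometric mean & CV% geometric mean will be presented by timepoints and treatment groups". No rule depends on time since the last dose.
- **Population.** SAP 7.3.5 requires medication compliance and a PK profile at all visits, and excludes patients with major deviations that affect PK results.
- **Last dose.** SAP 7.8 and 8.2.1 take the treatment end date from a last-dose date on the study completion or early termination page. It is a date, not a time.

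**The concern.** Delaying the morning dose yields a trough only while the patient is still dosing. A 28-day course, a window to Day 31 and an instruction to delay that morning's dose cannot all apply on the last days of the window. A visit inside its window is not a protocol deviation, so SAP 7.3.5 gives no clear ground for removing the sample.

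At stake is the trough summary for the trial's one secondary objective. A sample taken after one or two extra days without drug is not a trough. Averaged in as one, it lowers the geometric mean and inflates the geometric CV at that visit. The efficacy and safety analyses do not use these values.

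**Working it through.** The documents state no dose-to-sample interval, so there is no plan figure to reproduce. One check of the plan's own figures does agree: 2 supplies x 14 days = 28 days = 56 twice-daily doses, which matches the stated course.

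**Inputs from the documents:** twice-daily dosing for 28 days; Visit 3 on Days 25 to 31; Visit 2 on Days 11 to 17; two two-week supplies.

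**Assumptions:** doses at 08:00 and 20:00; first dose on the morning of Day 1 (alternative: the evening); draw at 08:00 (alternative: as late as 17:00).

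**Visit 3, dosing stopped after 56 doses.** Gap = draw time minus time of last dose.

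| First dose | Last dose | Draw Days 25-29 | Draw Day 30 | Draw Day 31 |
|---|---|---|---|---|
| Day 1, 08:00 | Day 28, 20:00 | 12 h | 36 h | 60 h |
| Day 1, 20:00 | Day 29, 08:00 | 12 h | 24 h | 48 h |

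A 17:00 draw adds 9 h, so the Day 31 gap runs from 48 h to 60 + 9 = 69 h. Only the last two days of the window are affected.

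**Visit 2.** Treatment does not end on Day 14, so a gap needs the first supply to run out. With exactly 28 doses from the morning of Day 1, the last is at 20:00 on Day 14, and draws on Days 16 and 17 are 36 and 60 h later. Dosing through the evening of Day 16 takes 32 doses, so 32 - 28 = 4 spare doses remove the gap.

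**Both visits in one patient.** If the first supply runs out and Visit 2 is on Day 17, the second supply of 28 doses covers Days 17 to 30 and ends at 20:00 on Day 30. A Day 31 draw is then 12 h post-dose. On supply alone, the full gap cannot occur twice in one patient.

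**Illustration of the bias at Visit 3.** Assume simple exponential decline with half-life t hours. A 36 h sample is 2^(-24/t) of the 12 h trough and a 60 h sample is 2^(-48/t). The geometric mean of N samples, of which a are at 36 h and b at 60 h, is multiplied by 2^(-(24a + 48b)/(Nt)).

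| Assumed t | 36 h sample | 60 h sample | Mean, none late | Mean, 1 of 40 on Day 31 | Mean, visits uniform over 7 days |
|---|---|---|---|---|---|
| 6 h | 6% | 0.4% | 100% | 2^(-0.2) = 87% | 2^(-72/42) = 30% |
| 12 h | 25% | 6% | 100% | 2^(-0.1) = 93% | 2^(-72/84) = 55% |
| 24 h | 50% | 25% | 100% | 2^(-0.05) = 97% | 2^(-72/168) = 74% |

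The 40 is the planned group size in SAP 7.6. Half-life and attendance are assumptions, so the table shows only how widely the effect can vary.

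**The case against.** The strongest reply is that dosing may in fact run to the visit. The schedule marks treatment at Visit 3, and SAP 8.5 tells participants to delay the morning dose there, not to omit it. Both suggest that a dose is still due. Dosing through the morning of Day 31 would be 61 doses, or 61/56 = 108.9% compliance, inside the 80% to 120% range of SAP 8.2.2. That stands as a reason to make the point conditional. It does not remove it, because both documents also state a 28-day duration and neither says what happens when Visit 3 is late.

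A reader might infer that supplies end on Day 14. The documents do not say so. A two-week supply without a capsule count leaves overage open, and the 120% compliance ceiling suggests, without proving, that spare capsules were issued. The Visit 2 part is therefore only conditional.

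A reader might also infer that the comparison of dose levels is distorted. Nothing supports this: allocation is randomised and blinded, no reason is given for visit timing to differ by arm, and an equal proportional loss in both active arms cancels in their ratio.

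Finally, only the synopsis and schedule of the protocol are available here. Dispensing quantities or dose-time capture may be set out in the full protocol or the CRF.

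**Conclusion.** The point holds for Visit 3, on the condition that dosing stops after 28 days as both documents state. An in-window draw on Day 30 or 31 is then about 36 or 60 h after the last dose, and SAP 8.5 summarises it with samples about 12 h post-dose. The Day 31 figure lies between 48 and 69 h depending on clock times.

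For Visit 2, Days 16 and 17, it holds only if the first supply had no overage.

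The bias in the trough summary is downward. It cannot be sized from the documents: it is zero if nobody attends on the last two days of the window, and otherwise depends on a half-life and a visit distribution that are not given. The large reductions in the uniform-attendance column above should not be read as an estimate.

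This affects a descriptive secondary analysis and is cheap to put right, so the SAP should be changed.

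**What to change.** Add to SAP 8.5:

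1. **Visit 3.** A sample enters the trough summaries only if the collected last-dose date is no earlier than the day before the draw. Use the date as recorded. SAP 7.8 replaces a missing date by the last visit date, and that substitute would pass the screen automatically. The rule works whichever way late visits were dosed: a patient who dosed up to the visit stays in, and one whose last dose was on Day 28 leaves if drawn on Day 30 or 31.
2. **Visit 2.** Screen samples drawn on Day 16 or 17 by study day and the capsule count, to find those taken after the first supply had run out.
3. **Hours.** Apply an interval in hours after the last dose only if a last-dose time was captured. Dates and capsule counts cannot verify one. For example, a last dose at 08:00 on Day 29 and a draw at 08:00 on Day 30 pass the date rule at 24 h.
4. **Excluded samples.** List them and plot them by actual time since last dose, to the precision available.

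Separately, the passages on the 28-day course, the two-week supplies, the visit windows, the treatment mark at Visit 3 and the delayed morning dose must be reconciled on whether dosing continues to the visit.

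The cost is SAP wording and one derivation from data already collected. A few samples leave the trough table.
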